Early use in 3 local Child Development Clinics suggested that the tool can help inform decision making around the need for further diagnostic assessment when used alongside parental history and information from other settings such as school questionnaires. In addition to information obtained from the questions within the tool, clinicians commented that they often obtained additional information around the child's interaction with themselves and with the tool. This experience, together with consultation with our wider team, including an academic expert in psychological testing, including Theory of Mind, ([name]), [name] (Head of OT, Royal Free), [name] (expert in use of digital technology in autism), and local parents, has allowed us to modify the story lines.

[figure not shown]

Figure 2. Affect recognition page

[figure not shown]
Figure 3. First Order Theory of Mind Test page adapted from Unexpected Contents False Belief Task.

Initial Pilot Study

(IRAS 217324 REC 16/LO/2138; HRA 201701014).

Pilot data, testing Pirates in 32 typically developing children (TD) attending a mainstream primary school (ages 4-11 years), and children attending the Child Development Centre following referral for possible ASD/social communication difficulties (ASD) showed a strong negative correlation (p<0.001) between number of errors and age (see figure 4), with most key stage one children (4-7.4 years) making 7 or fewer errors, and key stage two (7.5-11 years) less than 4. Taking data from children attending clinic for possible ASD in current study, suggests that most children where there were concerns about social communication were scoring at a higher level than this. Using the cut off scores identified in this study gave sensitivity 85%, specificity 92%, NPV 94%, PPV 79% which if confirmed in the proposed study would give a favourable performance in comparison with current screening tools such as the SCQ. By relating individual scores to these cut offs showed that typically developing children made a mean 1.9 (CI -2.5 to -1.3) fewer errors than the cut off, whilst children considered likely to have ASD clinically made a mean of 3.9 (CI 1.4 to 6.2) errors above the cut off, the difference being highly statistically significant (t test, p<0.00001). Children reported enjoying completing Pirates, whilst parents reported this increased their confidence in clinic assessment.

[figure not shown]

Figure 4. Total score compared to age in months

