Accuracy Parameters Protocol Version 2 29/9/17

a) Pilot study data only. b) includes data from early clinical use prior to pilot study

Aims and objectives

Test automated story with children in mainstream school, and with those already diagnosed with autistic spectrum disorder (ASD) in child development centres (CDCs).

- 1. Primary objective: Investigate parameters of screening tool in a group of 4 to 11 year old children, i.e. of primary school age, with known ASD; estimate discrimination from a group of children who are "typically developing", i.e. who do not have a clinical diagnosis of ASD.
- 2. Assess sensitivity/specificity of individual questions and relationship to age e.g. even typically developing younger children may not understand idiom.

Project design

Research methods

1. Sensitivity and Specificity of screening tool

User testing, two groups (children with a diagnosis of Autism Spectrum Disorder (ASD), typically developing children with no diagnosis (TD)) recruited to assess sensitivity of the automated story in a) a clinical environment (ASD, N=62), b) and in a school setting (TD, N=62).

Ethical approval

This has already been achieved for the initial pilot study in an investigation of typically developing children and children referred to a child development clinic for social communication difficulties (IRAS 217324 REC 16/LO/2138; HRA 201701014). We now hope to extend this to the proposed study through substantial amendment. The main change from the original pilot study is to change the "clinical group" from children referred for initial assessment of possible ASD to children already diagnosed with autism spectrum disorder. The methodology is essentially unchanged.

Subjects (including justification for sample size)

A sample of 124 children, suggested after consultation with Research Design service and Medical Statistician, with 62 typically developing children (31 male, 31 female), 62 with ASD (31 male, 31 female) aged 4 to 11 years will be recruited. With 62 children in each group, we will be able to further estimate the sensitivity and specificity of the software result with sufficient precision to enable us to isolate key parameters (Teare et al, 2014). For example, following Buderer (1996) with 62 ASD and 62 typical (i.e. a prevalence of ASD of 50%), assuming a sensitivity of 80%, the 95% confidence interval (CI) for sensitivity

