would be from 70 to 90%. The same applies for specificity. For this first stage, we aim to cluster children into two groups from the results of the application: "at risk/no risk" of ASD, which should match with ASD/No ASD. These two groups would then be further analysed against results to see if there is specific clustering around certain scores (total score, and for individual questions/sections), or responses, that may relate to other common associated impairments and co-morbid conditions which are: learning difficulty, language impairment, attention deficit hyperactivity disorder.

Recruitment

Children aged 4 to 11 years with ASD will be identified through CDCs in Sussex Community NHS Trust, by paediatric clinicians; typically developing children will be identified through the headteacher/appropriate member of staff in mainstream primary schools. The parents of children identified will be given a participant information sheet, and asked to contact the research team if they are interested in taking part. We estimate that we will need to approach 240 parents to achieve the full sample of 120 children. This is based on previous local recruitment rates for neuro-disability research of approximately 50% response. We will need to approach 12 potential recruits per month, with 6 recruited per month or 1.5 per week. This means the recruitment and data collection will be spread over 24 months, which we believe is feasible. We will aim to recruit and case match by age and gender.

Information leaflets will be given to the clinical group either in clinic by a member of the clinical care team or from the clinical team by post. Following this, parents will be contacted by the research team, and written informed consent will be sought. The pirate app testing will take place either in the home, clinic or school depending on adult preference.

Children in school will be given study information via school. Parents will then be contacted by the research team to discuss the study and if appropriate consent will be returned to school and then handed to research team. Phone contacts may be made to remaining parents to seek consent, where appropriate.

Inclusion criteria

Children aged 4 to 11 years, of primary school age:

- Group One: ASD: children with a recently confirmed diagnosis of ASD. Diagnosis will have involved full multidisciplinary diagnostic assessment by a CDC.
- Group Two: Typically developing group attending mainstream school

Exclusion criteria

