- Child non-verbal or severe learning difficulties or English as second language;
- Typically developing children with prior referral to a child development team or with known social communication or language difficulties or ADHD. These children may take part but results will not be included in typically developing results for analysis.
- Child not of primary school age (i.e. 4 to 11 years).

Process of gaining consent

All necessary consents will be obtained from parents and children following research ethical approval in advance of recruitment and data collection. Individual school policy will be followed for consenting and acceptability of school recruitment. A member of the team experienced in education will lead school recruitment (ex-Assistant Head teacher). Parental consent and child assent will be sought. Two schools in the local area have indicated interest in the study giving a potential recruitment base of 800 children.

Test

Participants in both groups will be given the screening tool to complete. A medical researcher will administer the application to children with ASD and typically developing children in clinic and/or in schools or in the child's home. The story produces pass/fail results recorded anonymously within the software. This data will be transferred to a paper record, and automatically deletes from the software once the individual testing is completed. Current cut-offs are set at 7 errors for key stage one children (4-7.4 YO) and 4 errors for key stage two (7.5-11YO). Results will be collated to attempt to see if it is possible for scores to cluster clearly around typical and ASD populations. There is already evidence of clustering for a clinically abnormal versus typically developing population.

Data analysis

Quantitative Analysis

The main aspects of data recorded will analyse the ASD group: SCQ score, clinical notes confirmation of ASD (yes/no), and automated story result (at risk of ASD yes/no using cut-off scores). Typically developing group will be scored only on automated story result (given that there has been no clinical contact). These will be used to assess sensitivity and specificity with three levels of cross sectional analysis:

- a) Clinical notes diagnosis (i.e. does school observation support diagnosis Yes/No) vs. automated story result
- b) SCQ score vs. automated story result
- c) SCQ score + clinical notes (i.e. does school observation support diagnosis Yes/No) vs. automated story result

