We will also calculate positive and negative predictive values. Sensitivity of the instrument with correct case finding will be based on clustering on types of ASD and typically developing children.

For this stage we aim to cluster children into two groups from the results: "at risk/not at risk" of ASD, which should match with ASD/Typically Developing.

These two groups would then go into secondary analysis to consider if there is clustering around certain scores or answers, and future study will explore relationship to other common associated impairments and co-morbid conditions such as: learning difficulty, language impairment, attention deficit hyperactivity disorder. We will estimate proportions of pass/fail recruited and retained for the clinical study and estimate sensitivity and specificity i.e. where sensitivity is the proportion of children with ASD that the tool correctly identifies, and specificity is the proportion without ASD that the screening tool correctly identifies. Thresholds and potential cut-off points for scores will be further clarified and defined using Receiver Operating Characteristic curves will to help refine the tool by comparing sensitivity/specificity and enable appropriate cut-offs to be decided. A logistic regression model will also be fitted to understand accuracy where the result of the tool is the predictor variable and we will also adjust for age and gender, as the at-risk of ASD and typically developing will be matched on these. If the tool detects accurately we will then aim to acquire European medical device regulation 93/42/EEC(MDD)8 for clinical trials [46]. If sensitivity/specificity trial is successful, the equipment will be used in a planned clinical trial.

Potential of research for patient care

Improving information at initial screening will reduce stress and anxiety for children and families and improve the experience and engagement of children. Further, quicker and better decision making will aid in determining which children require full assessment.

References

Autism Achieve Alliance (2014) Autism Spectrum Disorders: Waiting for assessment. Executive Summary, 6 August 2014 (accessed 26/2/2016)

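### The protocol does not say whether the pre-set or the ROC-refined cut-offs give the accuracy that decides success, and plans no validation or correction for the refined ones

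*Protocol*

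**What the plan says.** Four statements in the protocol bear on this.

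- **Cut-offs are set before data collection.** The Test section states: "Current cut-offs are set at 7 errors for key stage one children (4-7.4 YO) and 4 errors for key stage two (7.5-11YO". According to Initial Pilot Study, they come from the pilot.
- **They define the index-test result.** Data analysis (Quantitative Analysis) lists the "automated story result (at risk of ASD yes/no using cut-off scores" among the recorded data and says these data will be used to assess sensitivity and specificity.
- **They are then re-derived.** The same section continues: "Thresholds and potential cut-off points for scores will be further clarified and defined using Receiver Operating Characteristic curves". The stated purpose is to refine the tool and settle appropriate cut-offs. No second sample, cross-validation or bootstrap correction is described.
- **Decisions follow.** Still in that section, a device-regulation step is conditional on the tool detecting accurately, and "If sensitivity/specificity trial is successful, the equipment will be used in a planned clinical trial". Neither condition has a numerical criterion or names the cut-offs that it refers to.

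The precision claim is in Subjects. For 62 children per group and a true value of 80%, it says that the limits "would be from 70 to 90%. The same applies for specificity".

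**The concern.** A cut-off chosen because it separates two groups best in a sample will look better in that sample than in new children. The selection step capitalises on chance, so apparent sensitivity and specificity are biased upward, and the ordinary binomial interval ignores the selection.

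The protocol contains both a clean estimate (accuracy at 7/4 in children who did not set those cut-offs) and an estimate open to this bias (accuracy at cut-offs re-chosen by ROC in the same children). It does not rank them. If the refined cut-offs look better, as they usually will, nothing stops their apparent accuracy from being read as the study's answer to its primary objective and used to justify the device step and the next trial. The wording leans that way, since it calls the pre-set values current and then says they will be further defined.

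The pilot accuracy (85% and 92%) was itself quoted at cut-offs identified in the pilot. This study is therefore the natural first independent check, and the plan should protect it. Details of a correction method can be left to a statistical analysis plan. Which estimate answers the primary objective and drives the stated decisions is for the protocol, because the protocol itself states the accuracy analysis, the re-selection and the decisions.

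**Working it through.** **1. The plan's own precision figure.** Inputs from Subjects: n = 62 per group, p = 0.80, 95% two-sided.

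Half-width = 1.96 × √(p(1−p)/n) = 1.96 × √(0.16/62) = 0.0996, giving 70.0% to 90.0%.

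Inverting for ±10 points: 1.96² × 0.16/0.10² = 61.5, so 62 per group, and 62/0.5 = 124 in total. The stated figure reproduces. It is the interval for a proportion at a cut-off fixed in advance.

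**2. Accuracy at the pre-set cut-offs.** If 7 and 4 are fixed before the children are seen, the observed proportions are unbiased for the true sensitivity and specificity of that rule. Selection optimism is zero by construction, and step 1 applies. This requires that the pilot children who set the cut-offs are not counted in the 124. The protocol describes an extension of the pilot by substantial amendment and does not say this expressly.

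**3. Accuracy at ROC-chosen cut-offs.** No closed formula fits, so this was simulated with 20,000 studies per scenario. Errors relative to the cut-off were drawn as normal and rounded to integers. The cut-off maximising sensitivity + specificity (Youden) was chosen, and its accuracy in the same children was compared with its true accuracy. Two layouts were run: one cut-off for 62 v 62, and one cut-off per key stage with 31 v 31 in each.

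Pilot-like inputs come from Initial Pilot Study:

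- Typically developing: mean −1.9, CI −2.5 to −1.3. With n = 32, SD = 0.6/2.04 × √32 ≈ 1.7.
- ASD: mean +3.9, CI 1.4 to 6.2. The group size is not stated; n = 13 is inferred from the quoted 85/92/94/79%. SD = 2.4/2.179 × √13 ≈ 4.0.

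The other scenarios assume equal SDs in the two groups and a stated true accuracy.

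| Scenario | One cut-off: optimism, sens / spec (points) | One per key stage: optimism, sens / spec (points) |
|---|---|---|
| Pilot-like | 1.2 / 1.2 | 2.2 / 2.1 |
| True 80/80, SD 2 | 1.5 / 1.4 | 2.6 / 2.6 |
| True 80/80, SD 3 | 1.8 / 1.8 | 3.0 / 3.1 |
| True 70/70, SD 2 | 1.9 / 1.9 | 3.3 / 3.4 |
| True 90/90, SD 2 | 1.1 / 1.1 | 2.0 / 2.0 |

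In the pilot-like case with one cut-off per key stage, for example, apparent sensitivity is 80.3% against a true 78.1%, and apparent specificity is 94.3% against 92.2%. With true 80/80 and SD 4, optimism in the sum of the two measures is 4.1 points (one cut-off) and 6.6 points (one per key stage), or about 2.1 and 3.3 points each.

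**4. Interval coverage.** Under the pilot-like and true 80/80 scenarios, the nominal 95% interval for sensitivity + specificity at the chosen cut-offs covered the truth about 89-92% of the time with one cut-off and about 81-87% with one per key stage. The precision statement in step 1 therefore does not transfer to ROC-chosen cut-offs.

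**The case against.** **The natural reading is fixed cut-offs first, refinement second.** The protocol sets 7 and 4 in advance, defines the tool's result by cut-off scores, and says that result will be used for sensitivity and specificity. ROC comes afterwards and is described as refinement. Neither decision statement refers to ROC-derived values. This stands in part. A reader might infer that the figures triggering the next trial will be over-optimistic, and the document does not support that, because an unbiased estimate is also planned. What remains is that nothing makes that estimate the decisive one.

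**The bias is small.** Per measure it is about 1-3.5 points, against a planned interval of about ±10 points. Adding the two measures makes it look twice as large. This also stands and limits the weight of the point. The bias is nevertheless systematic and favours proceeding.

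**Correction methods belong in a statistical analysis plan.** That is fair for the choice between bootstrap and cross-validation. It does not cover the missing statement of which cut-offs count.

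**Age.** Initial Pilot Study says the data "showed a strong negative correlation (p<0.001) between number of errors and age", and Quantitative Analysis says "A logistic regression model will also be fitted to understand accuracy where the result of the tool is the predictor variable". A reader might infer that the ROC will pool raw scores over ages 4-11 and so distort the comparison, or that the logistic model wrongly uses the yes/no result. The documents do not support either criticism. No section states a pooled raw-score ROC. The current cut-offs are age-banded, the groups are to be matched on age and gender, and the logistic model adjusts for both. Pooling over age would also tend to understate discrimination, the opposite of optimism.

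**Conclusion.** The point holds as an ambiguity that leaves room for bias; it does not show that a biased figure will be used. The protocol plans accuracy at pre-set cut-offs and a re-selection of cut-offs in the same children, then rests two decisions on accuracy without saying which set is judged. No validation or correction is stated for the re-chosen set.

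If the ROC-chosen cut-offs are used, each of sensitivity and specificity could be overstated by about 1-2 points with a single cut-off, or about 2-3.5 points with one per key stage. The 70-90% precision statement would not apply. These sizes rest on normal-shaped integer scores, Youden selection and an equal key-stage split, none of which the protocol gives; other distributions or selection rules would change them. If the pre-set cut-offs are used in children not drawn from the pilot, there is no selection bias and the stated precision is correct.

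This is a worthwhile, inexpensive clarification and not a fatal flaw.

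**What to change.** In Quantitative Analysis, state the following.

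1. The primary result is sensitivity and specificity at the pre-set cut-offs (7 errors at 4-7.4 years, 4 errors at 7.5-11 years) in newly recruited children, with pilot children not counted. This result is the only basis for judging that the tool detects accurately and that the study has succeeded.
2. ROC-derived cut-offs are exploratory and are derived within key stage. Their accuracy is reported with a bootstrap or cross-validated correction that repeats the whole cut-off selection in each resample. They are carried forward for confirmation in new children.

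The cost is a change of wording and a few hours of programming, with no additional data. Reported accuracy at the refined cut-offs will be slightly less favourable.

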Situational Facial Recognition Pass/Fail Facial Expression Situational Ship captured Screen 13 Screen 15 Screen 15 Screen 15 Screen 15 Screen 15 Screen 17 Pass/Fail Control (language) same Parrots Screen 17 Parsots Screen 18 Parrots Screen 18 Pass/Fail Control (reality) Crab test What do the pirates think is in chest? Screen 25 What is in the chest? Screen 25 Pass/Fail Control Question (memory, naming) Who is Pirate Tom Screen 32 Control Question (memory naming) Who is Pirate Jimmy Screen 32 Control Question (memory naming) Who is Pirate Jimmy Screen 32 Control Question (memory naming) Where does Tom think the treasure is? Where does Tom think the treasure is? Where was the treasure in the beginning Where was the treasure in the beginning Pass/Fail Pass/Fail Pass/Fail Pass/Fail Pass/Fail Control (memory) Where was the treasure in the beginning? Screen 53 Screen 54 Where was the treasure in the beginning? Screen 55 Pass/Fail Question (comprehension) It's a lovely day. Telling truth Screen 60 Pass/Fail Question (comprehension) Spilt beerTelling truth Screen 66 Pass/Fail Question (comprehension) Spilt beerTelling truth Screen 67 Pass/Fail Comprehension Cost arm and leg Screen 70 Pass/Fail Comprehension Cost arm		Focus (none, pro	olonged)			
Pass/Fail Question (comprehension) Pass/Fail Question (comprehension) Pass/Fail Pass/Fail Question (comprehension) Sorteen (and the pass/Fail pass/Fail Question (comprehension) Sorteen (and the pass/Fail pass/Fail Question (comprehension) Spilt beerTelling truth pass/Fail Pass/Fail Question (comprehension) Spilt beerTelling truth pass/Fail Question (comprehension) Spilt beerTelling truth pass/Fail Pass/Fail Question (comprehension) Spilt beerTelling truth pass/Fail Pass/Fail Question (comprehension) Spilt beerTelling truth pass/Fail Sorceen 65 Sorceen 67 Pass/Fail Pass/Fail Question (comprehension) Spilt beerTelling truth pass/Fail Sorceen 67 Pass/Fail Pass/Fail Comprehension Cost arm and leg Sorceen 70	Seconds	Reaction time	Reaction time	Screen 10		
Pass/Fail Pass/Fail Control (language) same Parrots Screen 15 Screen 17 Pass/Fail Control (language) different Parrots Screen 18 Pass/Fail First order False Belief Test What do the pirates think is in chest? Screen 24 Chest? What is in the chest? Screen 25 Pass/Fail Control (reality) Crab test What is in the chest? Screen 25 Pass/Fail Control Question (memory, naming) Who is Pirate Tom Screen 32 Who is Pirate Immy Screen 33 Screen 34 Who is Pirate Immy Screen 33 Where does Tom think the treasure is? Where is the treasure really buried? Where is the treasure really buried? Where was the treasure in the beginning Where was the treasure in the beginning Pass/Fail Pass/Fail Pass/Fail Pass/Fail Pass/Fail Control (memory) Where was the treasure in the beginning Screen 53 Pass/Fail Pass/Fail Question (comprehension) Where was the treasure in the beginning? Screen 54 Where was the treasure in the beginning? Screen 55 Pass/Fail Question (comprehension) It's a lovely day. Telling truth Screen 66 Pass/Fail Question (comprehension) Spilt beerTelling truth Screen 66 Pass/Fail Screen 67 Pass/Fail Comprehension Screen 67 Pass/Fail Comprehension Cost arm and leg Screen 70 Pass/Fail		Situational Facial F	Recognition			
Pass/Fail Control (language) same Parrots Screen 17 Screen 18 Pass/Fail Pass/Fail Pass/Fail First Order False Belief Test What do the pirates think is in chest? Screen 25 Pass/Fail Control (reality) Crab test What is in the chest? Screen 25 Pass/Fail Control Question (memory, naming) Who is Pirate Tom Screen 32 Sally Ann (Hiding treasure) (1st order 17 ToM) Where does Tom think the treasure is? Where was the treasure really buried? Where was the treasure in the beginning Pass/Fail Pass/Fail Control (memory) Mere does sailor Jack think Screen 43 Screen 43 Pass/Fail Pass/Fail Pass/Fail Control (memory) Where was the treasure in the beginning Who is Pirate Jimmy Screen 42 Screen 43 Screen 44 Screen 45 Screen 46 Screen 47 Screen 47 Screen 48 Screen 49 Screen 59 Screen 60 Screen 60 Screen 61 Screen 61 Screen 66 Screen 67 Screen 66 Screen 67 Screen 60 Screen 67 Scree	Pass/Fail	Facial Expression	Ship captured	Screen 13		
Pass/Fail Control (language) different Parrots Screen 18 First Order Theory of Mind (ToM) Pass/Fail First order False Belief Test Control (reality) Crab test What do the pirates think is in chest? Pass/Fail Control (reality) Crab test What is in the chest? Screen 25 First Order False Belief Pass/Fail Control Question (memory, naming) Pass/Fail Control Question (memory naming) Pass/Fail Control Question (memory naming) Pass/Fail Control (reality) Pass/Fail Control (reality) Pass/Fail Control (reality) Pass/Fail Control (memory) Second Order Theory of Mind Pass/Fail Pass/Fail First order false belief Pass/Fail Control (memory) Where was the treasure in the beginning Where does sailor Jack think Tom thinks the treasure is? Where will Tom really look for the treasure? Where was the treasure in the beginning? Screen 53 Control (memory) Where will Tom really look for the treasure in the beginning? Where was the treasure in the beginning? First order false belief Where was the treasure in the beginning? Where was the treasure in the beginning? Screen 55 Higher Order Strange Stories 'Sarcasm' Pass/Fail Question (comprehension) Justification Why? Screen 66 Screen 67 Idioms Pass/Fail Comprehension Cost arm and leg Screen 70	Pass/Fail		Walk the plank	Screen 15		
Pass/Fail Control (language) different First Order Theory of Mind (ToM) Pass/Fail First order False Belief Test Control (reality) Crab test What is in the chest? Screen 25 First Order False Belief Pass/Fail Control (question (memory, naming) Control Question (memory naming) Sally Ann (Hiding treasure) (1st order TOM) Control (reality) Control (reality) Where does Tom think the treasure is? Where was the treasure really buried? Control (memory) Where was the treasure in the beginning Second Order Theory of Mind Pass/Fail Control (memory) Where was the treasure is? Where was the treasure is? Where will Tom really look for the treasure? Control (memory) Where was the treasure in the beginning? First order false belief Where was the treasure in the beginning? Where was the treasure in the beginning? Where was the treasure in the beginning? First order false belief Where was the treasure in the beginning? Where was the treasure in the beginning? Control (memory) Where was the treasure in the beginning? Where was the treasure in the beginning? First order false belief Where was the treasure in the beginning? Control (memory) Screen 53 First order false belief Where was the treasure in the beginning? First order false belief Screen 54 Where was the treasure in the beginning? Control (memory) Screen 60 Screen 55 Higher Order Strange Stories 'Sarcasm' Pass/Fail Question (comprehension) It's a lovely day Telling truth Screen 66 Pass/Fail Question (comprehension) Spilt beerTelling truth Why? Screen 67 Higher Order Strange Stories 'Lie' Pass/Fail Comprehension Comprehension Spilt beerTelling truth Screen 67 Idioms	Pass/Fail	Control (language) same	Parrots	Screen 17		
Pass/Fail First order False Belief Test Control (reality) Crab test What is in the chest? Screen 24	Pass/Fail		Parrots	Screen 18		
Pass/Fail First order False Belief Test Control (reality) Crab test What is in the chest? Screen 24			f Mind (ToM)			
Pass/Fail Control (reality) Crab test Chest? What is in the chest? Screen 25	Pass/Fail		1	Screen 24		
First Order False Belief Pass/Fail Pass/Fail Control Question (memory, naming) Control Question (memory naming) Who is Pirate Tom Screen 32 Screen 33 Pass/Fail Sally Ann {Hiding treasure} (1st order TOM) Where does Tom think the treasure is? Where is the treasure really buried? Where was the treasure in the beginning Screen 42 Dass/Fail Control (memory) Where was the treasure in the beginning Screen 43 Dass/Fail First order Theory of Mind (Mentalising) Where does sailor Jack think Tom thinks the treasure is? Where will Tom really look for the treasure? Where was the treasure in the beginning? Control (memory) Where was the treasure in the beginning? Screen 54 Where was the treasure in the beginning? Screen 55 Where was the treasure in the beginning? Screen 61 Dass/Fail Question (comprehension) It's a lovely day Telling truth Why? Screen 61 Dass/Fail Justification Why? Screen 65 Screen 67 Dass/Fail Justification Screen 67 Dass/Fail Justification Comprehension) Spilt beerTelling truth Screen 66 Pass/Fail Justification Comprehension Cost arm and leg Screen 70						
Pass/Fail Question (comprehension) Pass/Fail Pass/Fail Pass/Fail Question (comprehension) Pass/Fail Pass/Fail Pass/Fail Question (comprehension) Pass/Fail Pass/Fail Question (comprehension) Pass/Fail Pass/Fail Question (comprehension) Pass/Fail Pass/Fail Question (comprehension) Pass/Fail Question (comprehension) Pass/Fail Screen 67 Pass/Fail Pass/Fail Question (comprehension) Pass/Fail Screen 67 Pass/Fail Pass/Fail Question (comprehension) Pass/Fail Screen 67 Pass/Fail Pass/Fail Question (comprehension) Pass/Fail Screen 70 Pass/Fail Pass/Fail Pass/Fail Pass/Fail Question (comprehension) Pass/Fail Pass/Fail Pass/Fail Pass/Fail Question (comprehension) Pass/Fail P	Pass/Fail	Control (reality) Crab test	What is in the chest?	Screen 25		
Pass/Fail Question (comprehension) Pass/Fail Pass/Fail Pass/Fail Question (comprehension) Pass/Fail Pass/Fail Pass/Fail Question (comprehension) Pass/Fail Pass/Fail Question (comprehension) Pass/Fail Pass/Fail Question (comprehension) Pass/Fail Pass/Fail Question (comprehension) Pass/Fail Question (comprehension) Pass/Fail Screen 67 Pass/Fail Pass/Fail Question (comprehension) Pass/Fail Screen 67 Pass/Fail Pass/Fail Question (comprehension) Pass/Fail Screen 67 Pass/Fail Pass/Fail Question (comprehension) Pass/Fail Screen 70 Pass/Fail Pass/Fail Pass/Fail Pass/Fail Question (comprehension) Pass/Fail Pass/Fail Pass/Fail Pass/Fail Question (comprehension) Pass/Fail P						
Pass/Fail Pass/F		First Order Fals	e Belief			
Pass/Fail Sally Ann {Hiding treasure} (1st order TOM) Pass/Fail Control (reality) Pass/Fail Control (memory) Second Order Theory of Mind Pass/Fail Pass/Fail Pass/Fail Control (memory) Pass/Fail Pass/Fail Pass/Fail Control (memory) Pass/Fail Pass/Fail Pass/Fail Question (comprehension) Pass/Fail Pass/Fail Pass/Fail Pass/Fail Question (comprehension) Pass/Fail Pass/Fail Pass/Fail Question (comprehension) Spilt beerTelling truth Screen 66 Why? Screen 67 Screen 67 Pass/Fail Comprehension Screen 67 Screen 69	Pass/Fail	Control Question (memory, naming)	Who is Pirate Tom	Screen 32		
Pass/Fail Control (reality) Pass/Fail Control (memory) Second Order Theory of Mind Pass/Fail 2nd order Theory of Mind (Mentalising) Pass/Fail First order false belief Pass/Fail Control (memory) Where was the treasure in the beginning Where was the treasure is? Where does sailor Jack think Tom thinks the treasure is? Where will Tom really look for the treasure? Where was the treasure in the beginning? Screen 54 Where was the treasure in the beginning? Screen 55 Where was the treasure in the beginning? Screen 55 Where was the treasure in the beginning? Screen 56 Where was the treasure in the beginning? Screen 57 Pass/Fail Question (comprehension) Spilt beerTelling truth Screen 66 Why? Screen 67 Idioms Pass/Fail Comprehension Cost arm and leg Screen 70	Pass/Fail	Control Question (memory naming)	Who is Pirate Jimmy	Screen 33		
Pass/Fail Control (reality) Pass/Fail Control (memory) Second Order Theory of Mind Pass/Fail 2nd order Theory of Mind (Mentalising) Pass/Fail First order false belief Pass/Fail Control (memory) Where was the treasure in the beginning Where does sailor Jack think Tom thinks the treasure is? Where will Tom really look for the treasure? Where was the treasure in the beginning? Screen 54 Where was the treasure in the beginning? Screen 55 Higher Order Strange Stories 'Sarcasm' Pass/Fail Question (comprehension) Pass/Fail Comprehension Cost arm and leg Screen 70	Pass/Fail	Sally Ann {Hiding treasure} (1st order	Where does Tom think the	Screen 41		
Pass/Fail Control (memory) Second Order Theory of Mind Pass/Fail 2 nd order Theory of Mind (Mentalising) Pass/Fail 5 Pass/Fail 6 Pass/Fail 7 Pass/Fail 7 Pass/Fail 7 Pass/Fail 7 Pass/Fail 9 Pass/Fail 9 Pass/Fail 9 Pass/Fail 19 Pass/Fail 20 Question (comprehension) 19 Pass/Fail 20 Pass/Fail 30 Pass/Fail 30 Pass/Fail 30 Pass/Fail 30 Pass/Fail 30 Pass/Fail 30 Comprehension 30 Cost arm and leg 50 Screen 70		TOM)	treasure is?			
Pass/Fail Control (memory) Second Order Theory of Mind Pass/Fail 2nd order Theory of Mind (Mentalising) Pass/Fail First order false belief Pass/Fail Control (memory) Higher Order Strange Stories 'Sarcasm' Pass/Fail Question (comprehension) Pass/Fail Comprehension Cost arm and leg Screen 70	Pass/Fail	Control (reality)	Where is the treasure really	Screen 42		
Second Order Theory of Mind Pass/Fail 2 nd order Theory of Mind (Mentalising) Where does sailor Jack think Tom thinks the treasure is? Pass/Fail Control (memory) Where will Tom really look for the treasure? Pass/Fail Control (memory) Where was the treasure in the beginning? Screen 55 Higher Order Strange Stories 'Sarcasm' Pass/Fail Question (comprehension) It's a lovely day Telling truth Screen 60 Screen 61 Higher Order Strange Stories 'Lie' Pass/Fail Question (comprehension) Spilt beer Telling truth Screen 66 Screen 67 Justification Spilt beer Telling truth Screen 67 Idioms Pass/Fail Comprehension Cost arm and leg Screen 70	D 75 11		buried?			
Pass/Fail Question (comprehension) Screen 60 Pass/Fail Question (comprehension) Higher Order Strange Stories 'Lie' Pass/Fail Question (comprehension) Justification Australia Pass/Fail Question (comprehension) Justification Justification Justification Australia	Pass/Fail	Control (memory)	Where was the treasure in the	Screen 43		
Pass/Fail 2nd order Theory of Mind (Mentalising) Where does sailor Jack think Tom thinks the treasure is? Where will Tom really look for the treasure? Screen 54 Pass/Fail Control (memory) Where was the treasure in the beginning? Screen 55 Higher Order Strange Stories 'Sarcasm' Pass/Fail Question (comprehension) It's a lovely day Telling truth Screen 60 Screen 61 Higher Order Strange Stories 'Lie' Pass/Fail Question (comprehension) Spilt beerTelling truth Screen 66 Screen 67 Higher Order Strange Stories 'Lie' Pass/Fail Question (comprehension) Spilt beerTelling truth Screen 66 Screen 67 Idioms Pass/Fail Comprehension Cost arm and leg Screen 70			beginning			
Pass/Fail 2nd order Theory of Mind (Mentalising) Where does sailor Jack think Tom thinks the treasure is? Where will Tom really look for the treasure? Screen 54 Pass/Fail Control (memory) Where was the treasure in the beginning? Screen 55 Higher Order Strange Stories 'Sarcasm' Pass/Fail Question (comprehension) It's a lovely day Telling truth Screen 60 Screen 61 Higher Order Strange Stories 'Lie' Pass/Fail Question (comprehension) Spilt beerTelling truth Screen 66 Screen 67 Higher Order Strange Stories 'Lie' Pass/Fail Question (comprehension) Spilt beerTelling truth Screen 66 Screen 67 Idioms Pass/Fail Comprehension Cost arm and leg Screen 70						
Pass/Fail First order false belief Where will Tom really look for the treasure? Screen 54 Where was the treasure in the beginning? Screen 55 Screen 60 Screen 61 Screen 60 Screen 61 Screen 61 Screen 61 Screen 61 Screen 62 Screen 63 Screen 64 Screen 65 Screen 67 Screen 67		Second Order The	ory of Mind			
Pass/Fail First order false belief Where will Tom really look for the treasure? Screen 54 Control (memory) Where was the treasure in the beginning? Screen 55 Higher Order Strange Stories 'Sarcasm' Pass/Fail Question (comprehension) It's a lovely day Telling truth Screen 60 Screen 61 Higher Order Strange Stories 'Lie' Pass/Fail Question (comprehension) Spilt beerTelling truth Screen 66 Screen 67 Idioms Pass/Fail Comprehension Cost arm and leg Screen 70	Pass/Fail	2 nd order Theory of Mind (Mentalising)	Where does sailor Jack think	Screen 53		
Pass/Fail Control (memory) Higher Order Strange Stories 'Sarcasm' Pass/Fail Question (comprehension) Pass/Fail Comprehension Cost arm and leg Screen 70			Tom thinks the treasure is?			
